Uncontrolled BP is the leading preventable cause of death in the US after smoking, causing nearly 400,000 deaths per year¹. While effective medications are available to control BP, multiple rounds of medication adjustment and intensification are typically required, and BP control is often not achieved^{2,3}. The usual configuration of healthcare delivery – periodic and relatively infrequent office visits with a physician – is not ideal for achieving BP control quickly and efficiently^{4,5}. One promising approach to enhancing clinic-based BP management is to support home BP monitoring by patients⁶. Home BP monitoring technology has advanced substantially in recent years particularly in terms of linkage with Smartphones via Bluetooth, which enables use of associated Smartphone applications. Smartphone applications enable a wide variety of functions potentially useful for BP goal attainment, including reminders to measure BP, recording and displaying measurements, interpretation of measurements (e.g., goal attained, BP dangerously high, etc), and facilitating communication of measurements with treating clinicians. It is unclear, however, if this technological advancement helps patients achieve BP control. The PCORnet Home Blood Pressure Monitoring (BP HOME) Study is an individual-level randomized controlled trial that will compare the effectiveness of Smartphone-linked versus standard HBPM cuffs for helping patients with uncontrolled hypertension achieve a reduction in systolic blood pressure.

Aims

- 1) To compare the effectiveness of Smartphone-linked versus standard home BP monitors for helping patients with uncontrolled hypertension achieve a reduction in SBP.
- 2) To assess patient-reported outcomes including satisfaction with the HBPM device and various aspects of BP management
- 3) To assess the outcomes within subgroups based on age, sex and race/ethnicity.

Hypotheses

Patients with uncontrolled hypertension who receive a Smartphone-linked HBPM will have a larger average reduction in SBP at 6 months compared to those who receive standard HBPM, and will be more likely to promote use of the device to a friend.

Study Design

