Attachment D provides the text of the online surveys we will administer.

EHR data (all available data through end of follow-up will be extracted in the following domains)

Basic demographics

Diagnoses

Encounter characteristics

Provider characteristics

Blood pressure

Medications

Lab results

Death indicator

The EHR data analysis section, below, provides additional detail.

HBPM device data (all available measurements made during follow up, for Arm 1 only)

Blood pressure

Heart rate

Primary BP control outcome: The following pre-specified outcome will be used for the primary test of comparative effectiveness:

- 1) Reduction in SBP at 6 months. Reduction is defined by the absolute difference between the eligibility SBP (collected from the patient at the time of eligibility assessment), and the SBP measured at the most recent outpatient clinical encounter 6 months after enrollment. If more than 1 measurement is recorded during a single clinical encounter, the lower/lowest will be used.

Primary patient satisfaction outcome: The following pre-specified outcome will be used for the primary test of patient satisfaction:

- 2) Net Promotor Score. This score is assessed by asking a single question about likelihood of recommending the device to a friend, with options from 1-10 (10 being extremely likely). As per published methods^{7,8}, persons indicating 9 or 10 are considered "Promotors"; persons indicating 7 or 8 are "Passives"; and persons indicating 1-6 are

“Detractors”. The score is calculated by taking the percent of Promotors and subtracting the percent of Detractors, yielding a score for each group ranging from -100 to 100. Note that an identical score could theoretically be produced for a group with either a relatively high proportion of Promotors and Detractors, or a relatively low proportion of both.

Exploratory outcomes: The following pre-specified secondary outcomes will also be measured and analyzed. These include alternative measures of BP control, other patient-reported outcomes, and process measures intermediate along the causal pathway to BP control.

- 3) Documented attainment of a 10 mmHg reduction in SBP from baseline to 6 months, as defined above.

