- 4) Documented attainment of a 10 mmHg reduction in SBP at 6 months, as in Outcome 1, but assessed using home BP measurements, when available. As per guidelines, a set of 12 or more home measurements (counting no more than 2 in the morning and 2 in the evening of each day) within any given 1 week time period will count as a completed Home Measurement Protocol¹². The average SBP and DBP measurements within the most recent completed Home Measurement Protocol within 180 days of the index date (e.g., 6 months after enrollment) will then be used as the attained BP, regardless of subsequent clinic measurements or subsequent random home measurements. If no completed Home Measurement Protocol is available within 180 days of the index date, the most recent clinic measurement will be used. Note that a documented Home Measurement Protocol can only be attained in Arm 1, as home measurements will not be accessible in Arm 2.
- 5) Other BP Control outcomes defined as ((SBP<140 mmHg and DBP<90 mmHg) OR (SBP<130 and DBP<80) OR 10 mmHg reduction), assessed using the baseline measurement (self-reported OR last clinical measurement prior to randomization from the electronic health record) and subsequent measurements (clinical measurements OR clinical + home measurements) at a specified time-point (6 OR 12 OR 18 months) or using a time-to-control approach.
- 6) Patient reported outcomes including various aspects of satisfaction with the HBPM device and BP management, including quality of shared decision-making and patient activation.
- 7) Visit frequency. We will analyze the number of ambulatory care visits during the 6 month follow up period; we will also analyze the number of visits made before attainment of the first in-control BP.
- 8) Medication intensification. We will analyze the proportion of clinical visits with high BP (SBP>140 mmHg or DBP>90 mmHg) after which a BP medication was added.

Pre-specified subgroups: The following subgroups are pre-specified:

- Baseline Age: 20-44 vs 45-64 vs. 65+ years
- Sex: Male vs. Female vs. Other vs. Missing
- Race/Ethnicity: Non-Hispanic White vs. Non-Hispanic Black vs. Non-Hispanic Asian vs. Hispanic (any race) vs. Other/Multiple vs. Missing
- Subjective Social Status, measured through online survey at baseline, using MacArthur Scale for SES (not the “Community” version)⁹: Upper vs. Middle vs. Lower tertile, defined within our recruited sample of participants

Analysis Plan

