Exploratory analyses: We plan to analyze many additional outcomes, including alternate methods of defining BP control, alternate time-points, and additional endpoints including patient-reported outcomes and BP control process measures. These analyses are not planned for testing of the primary hypotheses, but are important for describing the experience of BP control using the two different device types and for generating hypotheses for future study. Our general approach to these analyses will be similar to how we approach the primary and secondary analyses, but we may use other methods that are not pre-specified.

EHR data analyses: We plan to analyze the EHR data obtained from each partner site. Each partner's EHR information is standardized to the PCORnet Common Data Model (CDM) to collect data from the EHR systems. The PCORnet CDM is a HIPAA Limited Data Set and quality checks of the EHR data are performed using procedures and algorithms that PCORI established

for its clinical data research network sites. Among other things, it standardizes laboratory tests and results using LOINC for laboratory tests and medication data using RxNorm.

Queries will be sent to the sites asking for the following data:

- Ambulatory Clinic information, including:
- Basic demographic and visit information
- Diagnoses
- Medication orders
- Blood pressure and pulse measurements
- Lab Reports relevant to blood pressure
- Vital Status

To obtain the information above, we will use the following tables from the PCORnet CDM:

- DEMOGRAPHIC
- ENCOUNTER
- PROCEDURE
- VITAL
- PRESCRIBING
- DIAGNOSIS
- LAB_RESULT_CM
- DEATH
- DEATH_CAUSE

Please note that the research team will NOT request release of information pertaining to drug and alcohol abuse, diagnosis or treatment; HIV/AIDS testing; genetic testing; or mental health diagnosis or treatment.

Attachment E summarizes the steps required for the OneFlorida Data Trust to obtain data for the queries.

Enrollment prediction modeling:

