In response to PCORnet's emphasis on ensuring access to health care interventions for vulnerable populations, we plan an exploratory post-hoc analysis examining any disparities in enrollment in BP HOME, particularly by race and ethnicity. Black and Hispanic/Latinx patients are underrepresented in clinical trials and health care research generally, and specifically within hypertension research. This is particularly worrisome given that these subgroups experience disproportionate burdens of negative sequelae of hypertension, including coronary artery disease, stroke, and chronic kidney disease. Further, the interaction between social determinants of health (SDH), Black race and Hispanic ethnicity, and participation in interventional trials is not well understood.

We plan to study the interaction between self-identified race, self-identified ethnicity, and various indicators of social determinants of health, measured at both the census tract and individual patient level, to understand their effects upon enrollment in BP Home. To accomplish this, participating BP Home sites will analyze all persons invited to join BP Home

and analyze predictors of enrollment. BP Home sites will consider different predictors depending on their availability; e.g., OCHIN may consider social determinants of health they have specified based on patient address and also at the individual patient level, while other sites may have different types of predictors. Sites will generally keep individual-level data on non-enrolled patients local and do analyses through their honest broker teams, sharing only model results (aggregated).

Multiple hypothesis testing: The intervention will likely be regarded as successful by clinicians if it is shown to be both efficacious and acceptable (that is, both co-primary outcomes are positive), so no penalty for multiple testing is needed to support this conclusion. In any case, the results of both hypothesis tests will be reported. No formal penalization for multiple hypothesis testing is planned for the subgroup or exploratory outcome analyses, which will be treated as exploratory and hypothesis-generating.

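### Exploratory item 8 measures medication intensification only at follow-up visits with high BP, so its arm difference is not a randomised comparison; a per-participant measure should stand beside it

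*Combined protocol and SAP*

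**What the plan says.** All references are to the combined protocol and SAP.

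- **Measurements, Exploratory outcomes, item 8.** The outcome is "the proportion of clinical visits with high BP (SBP>140 mmHg or DBP>90 mmHg) after which a BP medication was added". No time window is stated. It is read here as covering visits during follow-up, because it is listed as an outcome and the neighbouring item 7 uses 6 months.
- **Item 7.** "We will analyze the number of ambulatory care visits during the 6 month follow up period". Visit count is thus itself something the device may change.
- **Introduction to the exploratory outcomes.** They include "process measures intermediate along the causal pathway to BP control".
- **Hypotheses.** Patients given the linked device "will have a larger average reduction in SBP at 6 months compared to those who receive standard HBPM".
- **Background and Significance.** Among several potentially useful app functions is "facilitating communication of measurements with treating clinicians".
- **Analysis Plan, Exploratory analyses.** These serve for "describing the experience of BP control using the two different device types and for generating hypotheses for future study". On method: "Our general approach to these analyses will be similar to how we approach the primary and secondary analyses", with room left for methods not specified in advance.
- **Multiple hypothesis testing.** No adjustment is made for exploratory outcomes, "which will be treated as exploratory and hypothesis-generating".

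The EHR data analyses section requests medication orders and lists the PRESCRIBING table. No intensification measure over all randomised participants is named.

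**The concern.** A visit enters the denominator of item 8 only if it takes place and shows high BP. Both conditions arise after randomisation and both may respond to assignment. If the linked device lowers SBP, fewer Arm 1 patients have a high visit, and those who do are on average harder to control than their Arm 2 counterparts. If such patients have a different chance of receiving another drug, the two proportions differ even when clinicians act identically.

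The numerator has a gap as well. A drug added after home readings reach the clinician, with no earlier high clinic visit, is not counted. This could be more common in Arm 1.

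At stake is the explanation of the result: whether the device works through faster intensification. The measure could suggest a difference in clinician behaviour that does not exist, or hide added treatment that does.

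A separate matter of precision and weighting is that patients with many high visits count many times. That would be so without any device effect and is not itself a breach of randomisation.

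**Working it through.** **Plan's own figures.** None is given for item 8. The Sample size justification supplies only a scale for the device effect: 11 versus 10 mmHg with SD 8, that is 1/8 = 0.125 SD. With 1000 per arm and two-sided alpha 0.05 (assumed), power = Φ(0.125/√(2/1000) − 1.96) = Φ(0.835) = 0.798, which agrees with the stated 80%. This concerns the primary outcome and is used here only to fix 1 mmHg as the reference effect.

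**Main illustration (every rate assumed).** One follow-up visit per patient; only the SBP criterion is modelled; a drug is added only at a high visit; the prescribing rule is the same in both arms.

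- Visit SBP = μ + 6R + 12ε, with R (resistance) and ε standard normal. Total SD = √(36 + 144) = 13.42.
- μ = 142 in the standard arm; 141, 139 or 137 in the linked arm (device effect 1, 3 or 5 mmHg).
- P(high) = Φ((μ − 140)/13.42) = 55.9% in the standard arm; 53.0%, 47.0% and 41.2% in the linked arm.
- Mean R among patients with a high visit = 0.315 in the standard arm; 0.336, 0.378 and 0.423 in the linked arm. This is the selection.
- P(add | high visit, R) = 1/(1 + exp(1 − bR)), with b negative if resistant patients are less likely to receive another drug and positive if more likely.
- Visit-level rate = E[P(high | R) × P(add | R)] / E[P(high | R)]. Per-participant rate = the numerator alone.

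Differences, linked minus standard, in percentage points, by numerical integration over R:

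| b | Visit-level rate, standard arm | Visit-level difference, 1 mmHg | Visit-level difference, 5 mmHg | Per-participant difference, 1 mmHg | Per-participant difference, 5 mmHg |
|---|---|---|---|---|---|
| −0.8 | 24.6% | −0.28 | −1.46 | −0.88 | −4.23 |
| −0.4 | 25.1% | −0.15 | −0.79 | −0.82 | −4.04 |
| +0.4 | 30.0% | +0.16 | +0.87 | −0.80 | −4.07 |
| +0.8 | 33.9% | +0.32 | +1.72 | −0.83 | −4.30 |

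For scale, the standard error of the visit-level difference with 1000 per arm is √[p₀(1 − p₀)/(1000h₀) + p₁(1 − p₁)/(1000h₁)], where p is the visit-level rate and h is P(high). This is 2.6 to 2.9 points at 1 mmHg and 2.8 to 3.1 at 5 mmHg. The distortion is at most about 0.32/2.87 = 0.11 of a standard error at 1 mmHg and 1.72/3.10 = 0.55 at 5 mmHg.

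**Two other assumed set-ups.**

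1. *Same rule tied to the reading.* logit P(add) = −1.5 + 0.06(SBP − 140), visit SD 15. Mean 145 versus 144 gives 34.9% versus 34.4% (0.6 points before rounding); 145 versus 140 gives 34.9% versus 32.3% (2.7 points before rounding). With SD 12 or 18 the 1 mmHg shift is again about 0.6 points.
2. *Two patient types, half each.* P(add | high visit) is 0.45 in engaged and 0.20 in other patients, with two visits each, 60% high in the standard arm. The rate there is (0.6 × 0.45 + 0.6 × 0.20)/1.2 = 32.5%. If the device lowers the high share in engaged patients only, to 55%, 50%, 40% or 30%, the Arm 1 rate becomes 32.0%, 31.4%, 30.0% or 28.3%. A nominal 5% test allowing for patient clustering rejected in about 6%, 8%, 23% and 51% of 2000 simulated trials, against 4.5% with no device effect.

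The second set-up shows that the distortion can become material, but only where the device effect is large and concentrated in the patients most readily treated.

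**The case against.** **The plan already limits the claim.** Item 8 is exploratory and hypothesis-generating, the plan nowhere says that it yields a randomised effect, and other methods are allowed. This stands, and it keeps the point minor. It does not change the stated definition, and leave to use other methods is not a commitment to a measure over all participants.

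**High-BP visits are the natural denominator for asking whether clinicians act on a high reading.** This also stands. A reader might infer that a per-participant rate should replace item 8. The documents do not support that: item 8 asks about response to high BP, while a per-participant rate asks about total drug additions. In the main illustration the per-participant rate falls 0.8 to 4.3 points in Arm 1 under identical prescribing, further than the visit-level rate moves, merely because fewer patients had a high reading. It is a valid randomised contrast, but of a different quantity.

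**The distortion is small.** At the plan's own 1 mmHg example, it is about a tenth of a standard error or less in the main illustration. That is fair.

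**The missed between-visit additions are unquantified.** A reader might infer that prescribing between visits is the mechanism the app exists to enable. Background and Significance lists communication with clinicians as one of several possible functions, and both arms are told to deal with their physician as usual. Item 8 also sets no limit on how long after a high visit an addition may count, so some between-visit additions would be captured. Only those with no earlier high visit are lost.

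**Conclusion.** The point holds as a minor one. The arm difference in item 8 rests on visits selected after randomisation by variables the device may alter, so randomisation does not protect it, and additions with no preceding high clinic visit go uncounted. This needs only the possibility of a device effect; the effect itself is the trial's hypothesis, not an established fact.

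The main illustration puts the distortion at about 0.15 to 0.3 points for 1 mmHg and 0.8 to 1.7 points for 5 mmHg. Its sign depends on whether harder-to-control patients are more or less likely to receive another drug, which cannot be known in advance. The alternative set-ups give somewhat larger figures (about 0.6 points at 1 mmHg in one of them). All rest on assumed rates.

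A reader might infer that the trial's main findings are compromised. They are not: neither co-primary outcome uses item 8.

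**What to change.** 1. Keep the visit-level proportion as the measure of clinician response to high BP. State its time window, label the arm comparison descriptive and non-randomised, and account for repeated visits by the same patient; the primary model has a random effect for clinic but none for patient.
2. Beside it, add a measure in all randomised participants, taken from PRESCRIBING: any BP medication added within 6 months of randomisation (yes/no), and the number added. Use the primary model's random and fixed effects in a model suited to binary or count data.
3. Report the two together, noting that a lower per-participant rate in Arm 1 may reflect lower BP and not less responsive care.

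The cost is a modest amount of extra analysis on data already to be extracted. The drawback is that the per-participant measure mixes the need for intensification with its delivery, which is why it accompanies item 8 and does not displace it.

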We have designed a patient-level randomized controlled trial that will compare the effectiveness of Smartphone-linked versus standard HBPM for helping patients with uncontrolled hypertension achieve a reduction in their SBP, and patient satisfaction with the device. We aim to enroll 2000 patients who will be randomized in a 1:1 ratio to receive a Smartphone-linked or standard HBPM. We will use data from the electronic health record (EHR), an online patient portal, and the home BP monitor (in the Smartphone-linked arm) to collect outcome data for a period of at least 6 months (for the primary outcome), and up to 18 months (for secondary outcomes, depending on enrollment date). The primary BP control outcome will be reduction in SBP, by clinic measurements, at 6 months. The primary patient satisfaction outcome will be the Net Promotor Score^{7,8}, derived from self-reported likelihood of recommending the device to a friend, at 6 months.

Study Subjects

Target population

Adults receiving medical care who have uncontrolled BP

Accessible population

Adults receiving medical care at a participating PCORnet institution who meet inclusion criteria, are willing to enroll in the study, and complete baseline surveys.

Inclusion Criteria

- Age \geq 18 years
- At least one ambulatory visit in one of the participating study sites during the past year
- SBP > 145 mmHg at most recent clinic visit (may be treated with BP meds already or not), as reported by the participant
- A self-reported commitment to “work on lowering your blood pressure by 10 points or more to reduce your risk of heart attack and stroke”
- Owns a Smartphone (Android or iOS) and has an email address
- Willing to receive text messages from the study
- Can read/write English well enough to use English-based Smartphone apps and fill out online surveys in English

Exclusion Criteria

- Has an arm circumference <22 cm or >42 cm
- Owns a functioning HBPM and has used it in the last 3 months

Recruitment Plan

Participating sites will recruit patients via 2 basic methods.

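### The exploratory medication-intensification measure counts only added drugs, so a dose increase of an existing BP drug scores as no intensification

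*Combined protocol and SAP*

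**What the plan says.** In the protocol's Measurements section, under Exploratory outcomes, item 8 (Medication intensification) reads: "We will analyze the proportion of clinical visits with high BP (SBP>140 mmHg or DBP>90 mmHg) after which a BP medication was added". The words that set the numerator are "after which a BP medication was added". This is the only definition of intensification in the documents, and no other listed outcome measures treatment escalation. Item 7 counts visits. The opening of the same list describes some of its outcomes as "process measures intermediate along the causal pathway to BP control".

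Three other places bear on the definition:

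- **Inclusion Criteria.** The blood pressure criterion notes that participants "may be treated with BP meds already or not".
- **Background and Significance.** To reach control, "multiple rounds of medication adjustment and intensification are typically required".
- **EHR data analyses.** Medication orders and the PRESCRIBING table are requested from the sites, and the common data model standardizes "medication data using RxNorm". No rule is given for turning orders into an added drug.

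On status, the Exploratory analyses paragraph says "These analyses are not planned for testing of the primary hypotheses" and adds that "we may use other methods that are not pre-specified".

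**The concern.** The label and the numerator do not match. Because participants may already be on BP drugs at entry, treatment can be stepped up in at least two ways: a new drug is started, or the dose of a current drug is raised. Item 8 as worded sees only the first. A visit followed by a dose increase stays in the denominator and counts as a failure to intensify.

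The protocol leaves BP medication management to the treating clinician in both arms, and it names communication of readings to clinicians as a possible function of the app. Medication change is thus a plausible route from device to SBP. If the app works partly by prompting dose increases, the one process measure aimed at escalation would miss that part.

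What is at stake is how well a descriptive, hypothesis-generating result can be read. The primary comparison is not at stake.

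**Working it through.** **No plan figure to reproduce.** The documents state no expected intensification rate, effect size or power for item 8. The only power statement concerns SBP reduction. The check is therefore a reading of the definition, followed by an illustration in which every rate is assumed.

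**Reading the definition.**

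1. Numerator: a BP medication was added after the visit. A higher dose of a drug already prescribed is not, in ordinary usage, an added medication, so it is not counted.
2. Could dose increases occur in this population? Yes, because the Inclusion Criteria admit patients already on treatment.
3. Does another section widen the numerator? No. The EHR data analyses section names the data source but adds no definition.
4. Substitutions: nothing says whether the earlier drug must be continued. Replacing one drug with another might or might not count. This is silence in the text, unlike step 1, which follows from what is written.

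**Dose increases, equal share in both arms.** Let p be the true proportion of high-BP visits followed by intensification, and d the share of those that are dose increases only. Then

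measured proportion = p × (1 − d).

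| Assumed p, Arm 1 / Arm 2 | Assumed d, both arms | Measured, Arm 1 / Arm 2 | Difference (points) | Ratio |
|---|---|---|---|---|
| 40% / 34% | 0% | 40.0% / 34.0% | 6.0 | 1.18 |
| 40% / 34% | 30% | 28.0% / 23.8% | 4.2 | 1.18 |
| 40% / 34% | 50% | 20.0% / 17.0% | 3.0 | 1.18 |
| 30% / 25% | 0% | 30% / 25% | 5.0 | 1.20 |
| 30% / 25% | 20% | 24% / 20% | 4.0 | 1.20 |
| 30% / 25% | 40% | 18% / 15% | 3.0 | 1.20 |
| 30% / 25% | 60% | 12% / 10% | 2.0 | 1.20 |

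With d equal in both arms, the absolute difference is multiplied by (1 − d), while the ratio and the direction are unchanged.

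**Dose increases, share differing by arm.**

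- With p = 40% and 34%, and d = 50% and 35%: 0.40 × 0.50 = 20.0%, and 0.34 × 0.65 = 22.1%. The sign reverses.
- The break-even in that case: with Arm 2 at d = 35%, Arm 1's share must exceed 1 − 0.221/0.40 = 44.75% for the sign to change.
- With p = 30% and 25%, and d = 40% and 20%: 18% and 20%, a difference of −2.0 points.
- With those shares exchanged (d = 20% and 40%): 24% and 15%, a difference of +9.0 points. A differential share can therefore exaggerate the contrast as well as reverse it.

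**Substitutions.** Suppose they count as additions and occur after a proportion s of visits in both arms. With p = 30% and 25% and d = 0, s = 3% gives 33% and 28%, and s = 6% gives 36% and 31%. Both rates rise, and the difference stays at 5.0 points.

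**The case against.** The strongest reply is that little depends on item 8. It is exploratory, outside the tests of the primary hypotheses, and has no bearing on sample size or alpha. No mediation analysis is planned. A report accurately labelled as visits followed by an added drug would mislead nobody. The team already holds the orders and may use methods that were not pre-specified, so it could examine doses anyway. The Background sentence describes usual care and names adjustment and intensification as two things, so it does not oblige every adjustment to count.

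Most of this stands, and it limits the weight of the point. Two parts do not dispose of it. The outcome is labelled intensification, not drugs added, so the label promises more than the numerator delivers. And freedom to use other methods commits the team to nothing: a definition chosen after seeing data by arm is worth less than one fixed beforehand.

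It can also be said that "after which a BP medication was added" might be programmed as any new order, in which case some dose increases would be counted. That is not the plain meaning. If it is the intended one, it needs to be written down.

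A reader might infer that item 8 scores a switch as intensification. The documents do not say so. They are silent, and equal switch rates would leave the difference between arms unchanged.

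**Conclusion.** The point holds as a mismatch between what an exploratory outcome is called and what it counts. Dose increases score as no intensification, which can understate the rate in both arms and shrink the absolute difference. In the illustrations with equal shares, the difference falls from 6.0 to 4.2 or 3.0 points, or from 5.0 to between 4.0 and 2.0, with the ratio intact. These sizes rest wholly on assumed rates and on an assumed share of dose increases.

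A reader might go further and infer that the comparison would change direction, or that the trial would misexplain its SBP result. The documents do not support either. Reversal needs the dose-increase share to differ by arm by enough, and nothing in the protocol suggests any difference. The plan draws no causal conclusion from item 8, and neither co-primary result is touched. The change is worth making because it is specific and cheap.

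**What to change.** 1. Keep the added-drug measure as written, as the first component.
2. Add a second component: an increase in the ordered daily dose of a BP drug already prescribed, derived from the medication orders and PRESCRIBING table already requested.
3. Report each component, and the composite of either one, by arm.
4. Identify an added drug at ingredient level through RxNorm, so that a combination product containing a new ingredient counts as an addition.
5. Examine apparent one-for-one substitutions in a sensitivity analysis. A main rule requiring that no BP drug was stopped would depend on stop events that the documents do not say are captured. It would also misclassify a move to a combination product, or one drug replaced by two.
6. In the same edit, state the time window meant by an addition after a visit, which item 8 leaves open.

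The cost is the wording of one outcome definition and programming on data already being extracted, with no new participant contact. The downside is that some orders will lack a usable dose. Classify those visits on added drug only and report their number by arm, so that a reader can judge how far the dose component is still undercounted.
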